**Reason for Changes:**

These changes are being made to allow re-screening of subjects that have failed their initial screen but are believed to be eligible for enrollment if a second screen is completed, and to allow approval of enrolled subjects by email.

---

#### **Description of Changes:**

The purpose of this LOAC is to increase the upper age limit of the original protocol.

Inclusion Criterion #1 in Section 4.3 currently reads as follows:

1. Males, and females of nonchildbearing potential, between 18 and 65 years of age, inclusive, at Screening;

This LOAC revises Inclusion Criterion #1 to read as follows:

1. Males, and females of nonchildbearing potential, between 18 and 69 years of age, inclusive, at Screening;

The Synopsis will also be revised to reflect this change.

**Reason for Changes:**

This change is being made to allow Screening and inclusion of additional potential participants. Review of interim safety and tolerability data shows that doses of LOXO-292 were well-tolerated in subjects with hepatic impairment and healthy volunteers (age range 38 to 64 years old) with no Grade  $\geq 3$  toxicities reported.

---

#### **Description of Changes:**

This purpose of this LOAC is to clarify which serious adverse events (SAEs) should be reported. The last 2 sentences of the third paragraph of Section 7.2.1 on page 36 of the Protocol currently reads as follows:

All SAEs that develop from the time of ICF signing until Study Completion are to be reported. Following Clinic Discharge, only AEs or SAEs assessed as related to study drug should be reported

This LOAC revises SAE reporting to read as follows:

All SAEs that develop from the time of ICF signing until Study Completion are to be reported. Following Clinic Discharge through Study Completion, all SAEs must be reported and only AEs assessed as related to study drug should be reported.

#### **Reason for Changes:**

The change in SAE reporting is being made to eliminate contradictory information in the Protocol and to clarify that all SAEs should be reported.

---

3 ABBREVIATIONS

Abbreviations pertain to the SAP only (not the TFLs).

ADaM	analysis data model
AE	adverse event
ANCOVA	analysis of covariance
%AUC _{extrap}	percentage extrapolation for area under the concentration-time curve
AUC _{0-∞}	area under the concentration-time curve from time zero to infinity
AUC _{0-∞,u}	unbound area under the concentration-time curve extrapolated to infinity
AUC _{0-t}	area under the concentration-time curve from time zero to the time of the last quantifiable concentration
AUC _{0-t,u}	unbound area under the concentration-time curve from time 0 to the last measurable concentration
BLQ	below the limit of quantification
BMI	body mass index
CBC	Complete Blood Count
CDISC	Clinical Data Interchange Standards Consortium
CI	Confidence interval
CL/F	apparent systemic clearance
CL/F, _u	unbound apparent systemic clearance

C_{\max}	maximum observed plasma concentration
$C_{\max,u}$	unbound maximum observed concentration
CP	Child-Pugh
CSR	Clinical Study Report
CV%	coefficient of variation
EC	Early Clinical
ECG	Electrocardiogram
f_u	fraction unbound in plasma
ICF	Informed consent
ICH	International Conference on Harmonisation
LLOQ	lower limit of quantification
λ_Z	apparent terminal elimination rate constant
MedDRA	Medical Dictionary for Regulatory Activities
MRT_{last}	Mean residence time
NC	Not calculated
NR	No result
PE	Physical examination
PK	Pharmacokinetic
PT	preferred term

QTc	QT correction; QT interval corrected for heart rate
QTcF	QTc calculated using the Fridericia correction
SAE	Serious adverse event
SAP	Statistical Analysis Plan
SD	standard deviation
SOC	system organ class
$t_{1/2}$	apparent terminal elimination half-life
TEAE	treatment-emergent adverse event
TFLs	tables, figures, and listings
t_{max}	time to maximum observed concentration
V_d/F	apparent volume of distribution during the terminal phase
$V_d/F_{,u}$	unbound apparent volume of distribution during the terminal phase

4 INTRODUCTION

This SAP has been developed after review of the clinical study protocol (Final Version 1.0 dated 15 October 2018).

This SAP describes the planned analysis of the safety, tolerability and PK data from this study. A detailed description of the planned TFLs to be presented in the Clinical Study Report (CSR) is provided in the accompanying TFL shell document.

The intent of this document is to provide guidance for the statistical analyses of PK data. In general, the analyses are based on information from the protocol, unless they have been modified by agreement between Loxo Oncology, Inc. and Covance Early Clinical (EC) Biometrics. A limited amount of information concerning this study (eg, objectives, study design) is given to help the reader's interpretation. This SAP must be finalized prior to the lock of the clinical database for this study. When the SAP and TFL shells are agreed upon and finalized, they will serve as the template for this study's CSR.

This SAP supersedes the statistical considerations identified in the protocol; where considerations are substantially different, they will be so identified. If additional analyses are required to supplement the planned analyses described in this SAP, they may be performed and will be identified in the CSR. Any substantial deviations from this SAP will be agreed upon between Loxo Oncology, Inc. and Covance EC Biometrics and identified in the CSR.

The SAP is written with consideration of the recommendations outlined in the International Conference on Harmonisation (ICH) E9 guideline entitled, "Guidance for Industry: Statistical Principles for Clinical Trials" and the ICH E3 guideline entitled, "Guidance for Industry: Structure and Content of Clinical Study Reports."^{1,2}

5 STUDY OBJECTIVE

The objectives of this study are:

- To evaluate the PK profile of LOXO-292 in subjects with impaired hepatic function compared to matched-control healthy subjects;
- To evaluate safety and tolerability of LOXO-292 in subjects with impaired hepatic function and matched-control healthy subjects.

6 STUDY DESIGN

This study will be an open-label, nonrandomized, multi-center, single-dose, parallel-group, safety, tolerability, and PK study of LOXO-292 administered orally at a dose of 160 mg in fasted matched control healthy males and females with normal hepatic function compared to fasted, hepatically impaired subjects.

Subjects will be recruited in this study so that up to 24 subjects with hepatic impairment (up to 8 subjects within each of the mild, moderate, and severe impairment groups, per Child-Pugh [CP] classification – assessed at Screening and Check-in [Day -1]), and approximately 8 to 16 subjects with normal hepatic function are enrolled. Subjects will be enrolled within the following groups based on their CP score at Screening and assuming no change in underlying hepatic status at Check-in (Day -1) as judged by the Investigator (or designee), the Covance Medical Monitor, and the Sponsor:

- Group 1: Matched-control healthy subjects with normal hepatic function;
- Group 2: Subjects with mild hepatic impairment (CP Class A, score of 5 or 6);
- Group 3: Subjects with moderate hepatic impairment (CP Class B, score of 7 to 9);
- Group 4: Subjects with severe hepatic impairment (CP Class C, score of 10 to 15).

A parallel design strategy will be adopted for the hepatic impairment groups, with interim reviews of safety data after the first 4 subjects from Group 2 (mild hepatic impairment subjects), the first 4 subjects from Group 3 (moderate hepatic impairment subjects), and the first 2 subjects from Group 4 (severe hepatic impairment subjects) are enrolled and have completed all study-related assessments including the Follow-up phone call. Enrollment and dosing for remaining subjects in any group may occur after the interim data for that group are reviewed and the Covance Medical Monitor, Investigator (or designee), and Sponsor agree it is safe to proceed with dosing. If available, PK data and matched-control healthy subject data may also be used during the interim review.

[figure not shown]
Each matched-control healthy subject (Group 1) will be demographically matched (1:1) by age (\pm 10 years), body mass index (BMI; \pm 20%), and sex to the enrolled hepatic impairment subject(s). Should another hepatic impairment subject be identified with whom an already enrolled healthy subject is demographically matched, the healthy subject may also be matched with that impaired subject as long as the impaired subject is in a different hepatic impairment group. Each subject with normal hepatic function may be matched with up to 1 subject within each hepatic impairment group.

To assess their eligibility to enter the study, potential subjects will be screened within 28 days (Days -29 to -2) and be admitted to the clinical site on Day -1 (Check-in). Replacement subjects may be enrolled only if deemed necessary by the Sponsor.

Subjects will be confined at the clinical site from the time of Check-in (Day -1) until Clinic Discharge on Day 11 upon completion of all PK and safety assessments. A Follow-up phone call will occur approximately 7 days after Clinic Discharge.

On the morning of Day 1, after at least a 2-hour fast, an oral dose of 160 mg LOXO 292 administered as two 80-mg capsules will be given with 240 mL water. No food will be allowed for up to 1 hour postdose. Glucose tablets may be administered as needed for treatment of hypoglycemia.

Figure 1 Study design schematic

ICF = Informed Consent Form; PK = pharmacokinetic.

Note: Single oral dose of LOXO-292 at 160 mg administered orally after at least a 2-hour fast.

In this study design, physical examinations (PEs), 12-lead electrocardiograms (ECGs), vital signs, How Do You Feel? inquiries, clinical chemistry panel, coagulation parameters, complete blood count, and urinalysis will be performed at Screening and at specified times during the study. All adverse events (AEs) will be recorded throughout the study (ie, from signing of the ICF until Study Completion), either as subject medical history (if the event is reported as occurring prior to signing of the ICF) or as AEs (if the event occurs after administration of LOXO-292). Between the time of ICF signing to administration of LOXO-292 only AEs assessed as related to study procedures should be reported. All serious AEs (SAEs) that develop from the time of ICF signing until Study Completion are to be reported.

Study Completion is defined as the time of the last subject's Follow-up phone call.

7 TREATMENTS

The following is a list of the study treatment abbreviations and ordering that will be used in the TFLs

Hepatic Function Designation	Child-Pugh Classification	Study Treatment Name	Abbreviation	Order on TFLs
Normal Hepatic Function	< 5 points	Single dose of 160 mg LOXO-292	160 mg LOXO-292	1
Mild Hepatic Impairment	5 or 6 points (Class A)	Single dose of 160 mg LOXO-292	160 mg LOXO-292	2
Moderate Hepatic Impairment	7 to 9 points (Class B)	Single dose of 160 mg LOXO-292	160 mg LOXO-292	3
Severe Hepatic Impairment	10 to 15 points (Class C)	Single dose of 160 mg LOXO-292	160 mg LOXO-292	4

8 SAMPLE SIZE JUSTIFICATION

The sample size chosen for this study was based upon precedent set by other PK studies of similar nature and was not based on power calculations to detect statistically significant differences among groups. Six subjects each per hepatic function group are planned to complete the study. This is considered a sufficient sample size to evaluate the PK of LOXO-292 under various degrees of hepatic function.

9 DEFINITION OF ANALYSIS POPULATIONS

The **Safety Population** will consist of all subjects who received at least 1 dose of study drug (LOXO-292) and have at least 1 post dose safety assessment.

The PK population will comprise all subjects who comply sufficiently with the protocol and display an evaluable PK profile (e.g., exposure to treatment, availability of measurements and absence of major protocol violations). Samples from all subjects will be assayed even if the subjects do not complete the study. PK population will comprise all subjects who comply sufficiently with the protocol and display an evaluable PK profile (e.g., exposure to treatment, availability of measurements and absence of major protocol violations). A subject who experiences emesis at or before 2 times median Tmax for the given treatment during the PK sampling period time course may be excluded from the PK summary statistics and statistical analysis

All protocol deviations that occur during the study will be considered prior to database lock for their severity/impact and will be taken into consideration when subjects are assigned to analysis populations. Details of subject assignment to the analysis populations will be listed.

The **All Subjects Populations** will consist of any subjects who enrolled on to the study (signed informed consent, met all inclusion and exclusion criteria, and had study assessments recorded on the database as per the protocol).

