### 8.3. Analysis Populations

#### 8.3.1. Study Populations

The **PK Population** will consist of all subjects who have received a dose of LOXO-292, have at least 1 quantifiable plasma concentration, and for whom at least 1 PK parameter can be computed.

The **Safety Population** will consist of all subjects who received at least 1 dose of study drug and have at least 1 postdose safety assessment.

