12 CHANGES FROM THE PROTOCOL SPECIFIED STATISTICAL ANALYSES

The statistical methods for analysing the PK data outlined in the synopsis and main body of the protocol (version 1.0) and have been clarified in further detail in [Sections 10.4.2](#) and [10.4.3](#), including an additional analysis suitable for the hepatic design of the trial.

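### SAP section 9 replaces the protocol's objective PK Population with one that rests on undefined judgements and does not declare the change, so the primary ratios can depend on discretionary exclusions.

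*SAP*

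**What the plan says.** **Protocol.** Section 8.3.1 of the current version admits subjects who received a dose, "have at least 1 quantifiable plasma concentration, and for whom at least 1 PK parameter can be computed". The synopsis gives the same definition, and so does protocol version 1.0, from which the SAP was written. The amendment therefore does not explain the difference.

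**SAP section 9.** "The PK population will comprise all subjects who comply sufficiently with the protocol and display an evaluable PK profile". The only elaboration is a list of examples: "exposure to treatment, availability of measurements and absence of major protocol violations". A subject who vomits within 2 times the median tmax "may be excluded from the PK summary statistics and statistical analysis". Two safeguards follow: "All protocol deviations that occur during the study will be considered prior to database lock for their severity/impact", and "Details of subject assignment to the analysis populations will be listed".

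**Where the population is used.** SAP 10.1 runs the statistical analyses on the relevant population. The PK population therefore feeds the paired t-test in 10.4.2, which the SAP labels primary, and the ANCOVA in 10.4.3.

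**Declaring changes.** SAP section 4 says the SAP supersedes the protocol's statistical considerations and that "where considerations are substantially different, they will be so identified". SAP section 12 covers only the PK statistical methods of 10.4.2 and 10.4.3, "including an additional analysis suitable for the hepatic design of the trial". The population is not mentioned.

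**The concern.** The protocol's set can be rebuilt from the data by anyone. The SAP's set cannot, because membership turns on three terms with no definition and on an emesis clause whose trigger is numerical but whose consequence is optional. A dosed subject with computable Cmax and AUC is in under the protocol and may be out under the SAP.

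This matters because the groups are small. About 6 subjects per group are planned to complete and at most 8 impaired subjects per group are enrolled. In a paired analysis, losing either member removes the pair. One control may be matched to one subject in each of the three impairment groups, so excluding one control can remove a pair from all three comparisons. Protocol 1.4 says the study is meant to inform dosing recommendations in hepatic impairment. A reader of the report would not learn from SAP section 12 that the analysis set had changed.

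**Working it through.** The plan states no power, effect size or SD, so there is no figure to reproduce. The main check is textual; the arithmetic only shows scale.

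**1. Definitions side by side**

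| Element | Protocol 8.3.1 | SAP 9 |
|---|---|---|
| Dosed | required | example only (exposure) |
| Data available | at least 1 quantifiable concentration and 1 computable parameter | evaluable profile, not defined |
| Compliance | no criterion | sufficient, not defined |
| Protocol violations | no criterion | no major ones; major not defined |
| Early emesis | no criterion | optional exclusion |

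The substantive additions are the compliance and violation criterion and the emesis clause. Protocol 8.4 and 8.5 defer other data handling and specific statistical procedures to the SAP, but the protocol fixes the PK Population itself. The emesis cut-off is also unclear. It refers to the median for the given treatment, while SAP section 7 gives all four groups the same treatment name, so the median could be pooled or by group.

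**2. Effect of one excluded pair on the ratio**

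Let one of n pairs have a ratio k times the geometric mean of the other n - 1. Dropping it multiplies the estimated geometric mean ratio by k^(-1/n). The values of k are assumed; n = 6 and n = 8 come from the planned completers and the enrolment maximum.

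| Excluded pair | n = 6 | n = 8 |
|---|---|---|
| 2-fold above | 2^(-1/6) = 0.891 (-11%) | 2^(-1/8) = 0.917 (-8%) |
| 3-fold above | 3^(-1/6) = 0.833 (-17%) | 3^(-1/8) = 0.872 (-13%) |
| 2-fold below | 2^(1/6) = 1.122 (+12%) | 2^(1/8) = 1.091 (+9%) |
| 3-fold below | 3^(1/6) = 1.201 (+20%) | 3^(1/8) = 1.147 (+15%) |

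**3. Effect on the 90% confidence interval**

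The log-scale half-width is t(0.95, n-1) x SD / sqrt(n). The multipliers are 2.015/sqrt(6) = 0.823 for 6 pairs and 2.132/sqrt(5) = 0.953 for 5. Removing an outlying pair also lowers the SD. If the other five pairs have SD s, the six-pair SD is sqrt{[4s^2 + (5/6)(ln k)^2]/5}. With s assumed:

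| s | k | SD, 6 pairs | Half-width, 6 pairs | Half-width, 5 pairs | Ratio |
|---|---|---|---|---|---|
| 0.3 | 2 | 0.390 | 0.321 | 0.286 | 0.89 |
| 0.3 | 3 | 0.523 | 0.430 | 0.286 | 0.67 |
| 0.5 | 2 | 0.529 | 0.435 | 0.477 | 1.09 |
| 0.5 | 3 | 0.633 | 0.521 | 0.477 | 0.91 |
| 0.7 | 2 | 0.687 | 0.565 | 0.667 | 1.18 |
| 0.7 | 3 | 0.770 | 0.634 | 0.667 | 1.05 |

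The interval can move either way. The shift in the ratio is the firmer illustration, because it needs no SD.

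**The case against.** **The SAP governs.** It says it supersedes the protocol's statistical considerations, so a reader who infers that it had no authority to change the population goes too far. That is right. What remains is that the same sentence promises disclosure, section 12 does not give it, and the terms are undefined.

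**Sight of the data.** A reader might infer that only the SAP's set needs concentrations in hand, or that exclusions will be made by someone who has seen exposure. The documents do not support either. The protocol's own criteria also need concentration data, whereas compliance and violations can be judged without it. No section says when those assigning populations see concentrations. Open-label design adds little, since every subject gets the same drug and Protocol 3.3 calls the endpoints objective. The point that stands is narrower: nothing requires these decisions to be made blind to concentrations, and SAP section 11 allows PK data at interim reviews.

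**Safeguards.** Pre-lock consideration of deviations, listed assignments, excluded subjects highlighted in listings (SAP 10.1) and assay of all subjects' samples make exclusions visible. They are real protections, but they set no rule.

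**Likelihood.** Dosing is single, supervised and in clinic, and vomiting is not among the events above 10% reported in Protocol 1.3. Exclusions may be few or none.

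**The protocol set is itself too broad.** This stands. The drug appears to be metabolised primarily by CYP3A4 (Protocol 1.2), and Protocol 6.1 prohibits moderate or strong inhibitors and inducers unless approved. A subject who took one without approval would stay in the protocol set, and the SAP's parameter-level criteria would not necessarily detect it. A violation criterion is sensible, but it must be defined.

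**Conclusion.** The concern holds as an undeclared change from a checkable population to a judgement-based one that feeds the primary paired t-test and the ANCOVA. It is worth fixing before lock but is not fatal. The documents show that discretionary exclusion is possible, not that it occurred.

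At 6 pairs, one excluded pair that is 2- to 3-fold from the rest would move the geometric mean ratio by -11% to -17%, or +12% to +20%; at 8 pairs, by -8% to -13%, or +9% to +15%. These figures rest on the assumed 2- and 3-fold deviations, for which the documents give no basis. A reader might take the multipliers in the third step (0.953/0.823 = 1.16) to mean a 16% wider interval. That holds only if the SD is unchanged, which does not fit removal of an outlying pair; no direction should be claimed.

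Two other discretionary clauses lie outside this point and would remain: exclusion for high predose values (SAP 10.3.5) and case-by-case handling of outliers (SAP 10.4.2).

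**What to change.** 1. **SAP section 12:** declare that the PK population differs from Protocol 8.3.1, and why.
2. **SAP section 9:** start from the Protocol 8.3.1 definition. Allow exclusion only under a closed, pre-specified list of exposure-altering deviations, for example prohibited use of a CYP3A4 inhibitor or inducer, and say whether approved use counts. Decide from deviation records before concentrations are released, including release for an interim review.
3. **Emesis clause:** replace the optional wording with a fixed rule using one stated cut-off, the SAP's own 2 times median tmax, and state whether the median is pooled or by group. The cut-off needs concentration data, but a fixed rule leaves no choice in applying it.
4. **Sensitivity analysis:** run the paired t-test and the ANCOVA also on the unmodified Protocol 8.3.1 population, so that the effect of every exclusion can be seen.

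The parameter-level criteria in SAP 10.3.3 and 10.3.4 can stay as they are. The cost is SAP wording and one additional table; all subjects' samples are assayed in any case. The fixed emesis rule may remove a pair that the optional wording would have kept, and the sensitivity analysis shows what that does.

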10 STATISTICAL METHODOLOGY

10.1 General

Data listings will be provided for the All Subjects Population. Summary statistics and statistical analyses will be performed for subjects included in the relevant analysis populations (Safety/PK).

For continuous data, summary statistics will include the arithmetic mean, arithmetic standard deviation (SD), median, minimum, maximum, and number. For log-normal data (eg, the PK parameters: areas under the concentration-time curve [AUCs] and maximum observed concentration [Cmax]), the geometric mean and geometric coefficient of variation (CV%) will also be presented. For categorical data, frequency counts and percentages will be presented. Data listings will be provided for all subjects up to the point of withdrawal, with any subjects

excluded from the relevant population highlighted. For the calculation of summary statistics and statistical analysis, unrounded data will be used.

Missing values will not be imputed.

Data analysis will be performed using SAS® Version 9.4.

Analysis Data Model (ADaM) datasets will be prepared using Clinical Data Interchange Standards Consortium (CDISC) ADaM Version 2.1, and CDISC ADaM Implementation Guide Version 1.1. Pinnacle 21 Community Validator Version 2.2.0 will be utilized to ensure compliance with CDISC standards.

